### **Sensitivity Analysis**

Progression-free survival defined by the BICR in the FAS will be analysed as described for the investigator-assessed PFS endpoint (see above). Further sensitivity analyses will be described in the SAP.

### **Duration of Response**

The DoR is defined as the time from the date of first documented response until date of documented progression or death in the absence of PD (ie, date of PFS event or censoring – date of first response + 1). The end of response should coincide with the date of progression or death from any cause used for the PFS endpoint. The time of the initial response will be defined as the latest of the dates contributing towards the first visit response of CR or PR.

If a patient does not progress following a response, then their DoR will use the respective PFS censoring time.

If there are sufficient numbers of responders, and sufficient numbers of responses that have progressed by the point of the analysis, Kaplan-Meier plots of DoR in the responding patient will be produced and appropriate descriptive summary statistics will be presented (n, number of responses that have progressed, median, quartile, minimum and maximum DoR) by treatment group without any formal comparison or p-value attached.

### **Percentage Change from Baseline in Tumour Size**

Tumour size assessment is defined as the percentage change in TLs at 12 weeks per RECIST 1.1. Absolute change and percentage change from baseline in TL's tumour size at 12 weeks will be based on RECIST TLs measurements taken at baseline and at Week 12. Tumour size is the sum of the longest diameters of the TLs. Baseline for RECIST is defined as the last evaluable assessment prior to randomisation.

The percentage change in TL tumour size at Week 12 will be obtained for each patient by taking the difference between the sum of the TLs at Week 12 and the sum of the TLs at baseline divided by the sum of the TLs at baseline times 100 (ie,  $[\text{Week 12} - \text{baseline}] / \text{baseline} \times 100$ ).

The absolute change in TL tumour size at Week 12 will be obtained for each patient by the difference between the sum of the TL at Week 12 and the sum of the TL at baseline.

The absolute change in TL tumour size from baseline and percentage change in TL tumour

size from baseline will be summarised using descriptive statistics by randomised treatment group. Best percentage change will also be summarised.

The effect of study interventions on absolute and percentage change in TL tumour size will be estimated from an ANCOVA model including a term for treatment, the absolute (percentage) change in Week 12 value, a covariate for baseline TL tumour size, stratification used in randomisation, and a covariate for the time from the baseline scan to randomisation. The number of patients, unadjusted mean and least-squares means for each treatment group should be presented, together with the difference in least-squares means, 95% CI and corresponding p-value.

Handling of missing data will be described in the SAP.

Waterfall plots showing the percentage change at Week 12 and the best percentage change from baseline in sum of the diameters of TLs will be produced. Spider plots showing the actual change and the percentage change from baseline in tumour size for each patient over time may be produced.

Model checking diagnostics for the ANCOVA will be described in the SAP. If ANCOVA is deemed not to be appropriate, non-parametric techniques will be used. Further details in this regard will be described in the SAP.

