## 8.1 Efficacy Assessments

### 8.1.1 CT and MRI Scans Tumour Assessments (RECIST 1.1)

The RECIST 1.1 guidelines for measurable, non-measurable, TLs and NTLs and the objective tumour response criteria are presented in [Appendix H](#) of this CSP.

Baseline tumour assessments should include CT/MRI of chest and abdomen (including liver and adrenal glands) and should be performed within 28 days of randomisation, and ideally as close as possible to the start of study intervention. At screening the MRI/CT scans will include brain imaging for all patients. Those determined to have brain metastases will have their brain rescanned at all subsequent tumour assessments. Any other regions suspected, or with known metastasis at baseline, will be assessed by imaging and recorded at baseline. The same imaging modality used for baseline tumour assessment should be used for each subsequent follow-up assessment throughout the study if possible. Further details of the CT and MRI acquisition parameters will be documented in a separate image acquisition guidelines document.

Follow-up assessments should be performed Q6W ( $\pm 7$  days) after randomisation until Cycle 7 (up to 24 weeks), and then Q8W ( $\pm 7$  days) until objective PD as defined by RECIST 1.1 even if a patient discontinues treatment prior to progression (unless they withdraw consent). For patients who cross-over based on confirmed objective disease progression during the initial randomised treatment period (including patients who have already crossed over based on confirmed PD prior to CSP Version 3.0), scheduled RECIST 1.1 tumour assessments are not required, and the subsequent assessment of disease progression will be based on standard-of-care scan or investigator determined clinical progression. Scheduled RECIST 1.1 tumour assessments are required (the scan frequency is against initial randomisation) for patients who cross-over after study unblinding and who have not objectively progressed during the initial randomised treatment period. Patients who cross-over after study unblinding, who have no objective progression during initial randomisation period, and who discontinue study intervention after cross-over for reasons other than investigator-confirmed disease progression will continue scheduled RECIST 1.1 tumour assessments until objective disease progression per RECIST 1.1 as assessed by investigator, unless they withdraw consent to the entire study.

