#### **9.4.2.1 Analysis of Primary Endpoint**

Objective response rate by investigator assessment in accordance with RECIST 1.1 is the primary endpoint for this study.

The ORR is defined as the proportion of patients with an investigator-assessed response of CR or PR by RECIST 1.1.

Data obtained up until progression, or last evaluable assessment in the absence of progression, will be included in the assessment of ORR. Patients who discontinue treatment without progression, receive a subsequent anti-cancer therapy (note that for this analysis radiotherapy is not considered a subsequent anti-cancer therapy) and then respond will not be included as responders in the ORR.

The ORR will be analysed using a logistic regression model adjusting for the stratification used in the randomisation. The results of the analysis will be presented in terms of an odds ratio (an odds ratio greater than 1 will favour savolitinib in combination with osimertinib versus savolitinib in combination with placebo) together with its associated profile likelihood 95% CI and p-value (based on twice the change in log-likelihood resulting from the addition of a treatment factor to the model).

If there are not enough responses for a meaningful analysis using logistic regression then a CMH test will be presented.

Summaries will be produced that present the number and percentage of patients in each treatment group with a tumour response (CR/PR).

A sensitivity analysis of the ORR will be performed based on the BICR assessment of disease progression by RECIST 1.1. Further sensitivity analyses will be described in the SAP.

Summaries will be produced that present the number and percentage of patients in each treatment group with a tumour response (CR/PR). Summaries will also be produced for ORR per BICR.

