### Special Cases for TL Assessment at Follow-up

- If a lesion has completely disappeared, the diameter should be recorded as 0 mm. If a lesion appears in the same location on a subsequent scan, it will be recorded as an NL.
- If a TL splits into 2 or more parts, the sum of the diameters of those parts should be recorded.
- If 2 or more TLs merge, then the sum of the diameters of the combined lesion should be recorded for one of the lesions and 0 mm recorded for the other lesion(s). If the merged TLs are non-nodal lesions, record the long axis diameter of the merged lesion. If pathologic lymph nodes coalesce and are no longer individually separable within a conglomerate mass, the maximal short axis diameter is recorded.
- If a TL is believed to be present and is faintly seen but too small to measure, a default value of 5 mm should be assigned. If an accurate measure can be given, this should be recorded, even if it is below 5 mm.
- If a TL cannot be measured accurately due to it being too large, provide an estimate of the size of the lesion. The choice of “Too large to measure” in the case report form will trigger an overall visit response of PD.
- When a TL has had an unscheduled, non-protocol intervention, the following apply:
  - Target lesion intervention may include radiotherapy, embolisation, excisional biopsy, surgery, etc, that is not a part of study intervention and might adversely affect the size of that TL
  - If an Intervention on a TL is ticked in the CRF, the diameter of the lesion is still recorded (0 mm if no longer present) and is included in the sum of diameters.
  - If a TL Intervention is ticked, the intervention must be reported for all subsequent assessments of that TL.
  - If a TL has an Intervention, the only overall visit responses allowed to be recorded by the investigator are NE or PD, with PD if the sum of diameters exceeds a 20% increase and at least a 5 mm absolute increase in the visit sum of diameters compared to the previous minimum (nadir) sum of diameters.
  - No visit with a recorded Target lesion intervention can be used as the minimum (nadir) sum of diameters.

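### Section 9.4.2.2 does not exclude visits with a target-lesion intervention from Week 12 and best percentage change, so read literally a removed or irradiated lesion counts as tumour shrinkage

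*Supplement*

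**What the plan says.** **The endpoint.** Section 9.4.2.2 (Percentage Change from Baseline in Tumour Size) states that the change at 12 weeks "will be based on RECIST TLs measurements taken at baseline and at Week 12". It takes the difference between the two target-lesion sums, divided by the baseline sum. It then says: "Best percentage change will also be summarised". The Week 12 values feed an ANCOVA with a difference in least-squares means, a 95% CI and a p-value. Waterfall plots show both the Week 12 and the best change. The section requires an evaluable assessment for baseline but says nothing similar for later visits. Missing data, model diagnostics and the choice of non-parametric methods are left to the SAP, which is not among the documents shown.

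**The recorded sum.** Appendix H 2.9.1 (Special Cases for TL Assessment at Follow-up) defines the event: "Target lesion intervention may include radiotherapy, embolisation, excisional biopsy, surgery, etc, that is not a part of study intervention". For a lesion flagged in this way, the rule is: "the diameter of the lesion is still recorded (0 mm if no longer present) and is included in the sum of diameters". It must then be reported at every later assessment of that lesion.

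**The safeguards.** For a lesion with an intervention, H 2.9.1 says "the only overall visit responses allowed to be recorded by the investigator are NE or PD". It also says: "No visit with a recorded Target lesion intervention can be used as the minimum (nadir) sum of diameters". Table H2 makes the target-lesion response itself NE at such a visit, unless the PD criteria are met.

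**The concern.** The appendix leaves an artificially reduced sum in the data and, for response and for the nadir, stops it from being read as shrinkage. The tumour-size endpoint uses the same sum, and its section mentions neither safeguard. A visit that cannot support a response, and cannot serve as the reference minimum, could still supply the patient's Week 12 value. It could also supply the best change. The reduced lesion stays in the sum at all later visits, and best change looks for the smallest value.

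At stake is a secondary efficacy endpoint with a between-arm estimate and p-value. The achieved sample is also smaller than planned, so single patients carry more weight. The waterfall plot could show deep shrinkage for a patient whose visit is NE in the response analysis.

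**Working it through.** The plan gives no figure to reproduce here. The check sets the rules side by side and then sizes the effect on assumed lesions.

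**1. Which rule reaches which endpoint**

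| Rule | Response (ORR) | Nadir for progression | Week 12 change | Best % change |
|---|---|---|---|---|
| Visit with an intervention is NE or PD (H 2.9.1, Table H2) | Stated | – | Not stated | Not stated |
| Such a visit cannot be the nadir (H 2.9.1) | – | Stated | Not relevant: Week 12 is a fixed visit, not a minimum | Could be read across; not stated |
| Lesion stays in the sum (H 2.9.1) | Overridden by NE | Overridden by the bar | Applies | Applies |

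Borrowing the ORR rule on later therapy would not close the gap. Section 9.4.2.1 expressly does not count radiotherapy as a subsequent anti-cancer therapy. For ORR, an irradiated target lesion is caught by the NE rule. For tumour size, no stated rule catches it.

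**2. One patient**

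Formula (9.4.2.2): (Week 12 sum − baseline sum) / baseline sum × 100.

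Assume two target lesions of 40 and 30 mm, so the baseline sum is 70 mm. The 40 mm lesion is excised and recorded as 0 mm; the other is unchanged.

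- As recorded: (30 − 70)/70 × 100 = −57.1%.
- On the untouched lesion: (30 − 30)/30 × 100 = 0%.
- Under Table H2 the target-lesion response is NE.

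Other assumed splits, with a baseline sum of 80 mm and the remaining lesion unchanged:

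| Lesion removed | Recorded change |
|---|---|
| 20 mm | (60 − 80)/80 = −25.0% |
| 30 mm | (50 − 80)/80 = −37.5% |
| 40 mm | (40 − 80)/80 = −50.0% |
| 60 mm | (20 − 80)/80 = −75.0% |

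The sign can even reverse. If the 30 mm lesion is removed and the 50 mm lesion grows by 10% to 55 mm, the recorded change is (55 − 80)/80 = −31.25%, while the only untouched lesion has grown.

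**3. The arm mean**

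Shift in the unadjusted arm mean = individual distortion / n. The distortion is measured against no change in that patient. The planned 28 per arm will not be met (Section 9.2) and the achieved number is not given, so 10 to 28 is an assumed range.

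| n per arm | One patient at −57.1 | Two such patients |
|---|---|---|
| 10 | −5.7 points | −11.4 points |
| 20 | −2.9 points | −5.7 points |
| 28 | −2.0 points | −4.1 points |

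For distortions of 30 to 75 points, one patient moves the mean by 3.0 to 7.5 points at n = 10 and by 1.1 to 2.7 points at n = 28. The shift in the ANCOVA least-squares mean would differ somewhat because of covariate adjustment.

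**The case against.** **The SAP may already settle this.** Section 9.4 calls itself a summary, and visit-level derivations are often left to a SAP. That stands as a reason to accept confirmation in the SAP as a full remedy. It does not remove the point, which rests on two affirmative protocol rules (keep the lesion in the sum; compute change from the sum) and not on silence alone. The topics that 9.4.2.2 passes to the SAP do not clearly include it, since a recorded sum is not on its face a missing value.

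**Table H2 and the nadir bar arguably cover it already.** The endpoint is defined per RECIST 1.1, a target-lesion response of NE could be treated as non-evaluable, and best change is naturally taken from the smallest sum. This is a reasonable reading and the one the fix adopts. But 9.4.2.2 works from sums, not from response categories, and the nadir bar cannot reach the fixed Week 12 visit.

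**The example is assumed.** No document gives a rate of such interventions, and the patients have locally advanced or metastatic disease not amenable to curative therapy. This stands: the figures show what one patient could do, not what is expected.

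**Stakes are limited.** The endpoint is secondary, multiplicity is not controlled, no labelling claim is intended, and the primary ORR is protected. This also stands.

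**A stronger reading to avoid.** A reader might infer that shrinkage under a later anti-cancer therapy is also credited to study drug. Scans continue "even if a patient discontinues treatment prior to progression (unless they withdraw consent"), and the rule that patients who receive another therapy "and then respond will not be included as responders in the ORR" is written for ORR only. The documents do not show that such sums are used. Section 9.4.1 cuts off savolitinib plus placebo data before the first combination dose, and scheduled scans in the randomised period stop at objective progression. Excluding what remains is an estimand choice: PFS, for example, counts events regardless of other therapy. That handling should be confirmed in the SAP, but it is not a demonstrated error.

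**Conclusion.** The point holds for target-lesion interventions. As written, Section 9.4.2.2 and Appendix H 2.9.1 together let a lesion treated outside the protocol count as shrinkage in the Week 12 ANCOVA and the waterfall plots, and probably in best percentage change, although the protocol disqualifies the same visit for response and as nadir.

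The size is conditional. With the assumed 40 and 30 mm lesions, one patient is recorded at −57.1% and moves an arm mean by 2.0 points (n = 28) to 5.7 points (n = 10). Lesion sizes, achieved numbers and the frequency of interventions are all assumptions or unknown.

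Two further inferences are not supported. Nothing says that every recorded sum is used; the section simply states no exclusion. It is also tempting to expect more interventions in the arm doing worse, and so a treatment difference pulled towards zero. No document gives data on this, the distortion can occur in either arm, and its net direction is unknown.

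**What to change.** Add a sentence to Section 9.4.2.2, or confirm in the SAP before unblinding, along these lines: visits with a recorded target-lesion intervention are not evaluable for Week 12 change or best percentage change; a Week 12 value excluded for this reason is handled under the SAP missing-data rule. Optionally, repeat the ANCOVA with these visits included as a sensitivity analysis. In the same place, state how assessments after a later anti-cancer therapy are handled, as an explicit estimand choice.

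The CRF already flags interventions, so the work is one derivation rule and a programming filter, with no new data. The downside is that a few Week 12 values become missing, possibly for reasons related to outcome. The missing-data rule should therefore be fixed with that in mind.

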### **Overall Survival**

Overall survival is defined as the time from randomisation until death due to any cause, regardless of whether the patient withdraws from randomised therapy or receives another anticancer therapy. Any patient not known to have died at the time of analysis will be censored based on the last recorded date on which the patient was known to be alive.

Note: Patients will be contacted for survival follow-up Q12W until death, withdrawal of consent, or the end of the study ie, at the time of final analysis, defined as the earlier of 18 months after the last patient is randomised or when 70% of patients have progressed or died. Patients should be contacted in the week after DCO for each analysis to establish survival status. If patients are confirmed to be alive or if the death date is after the DCO date, these patients will be censored at the date of the DCO.

Overall survival will be analysed as described for the investigator-assessed PFS endpoint (mentioned earlier in this section). CCI

Further details will be provided in the SAP.

Summaries of OS (n, events, medians, quartiles, proportion alive at 3, 6, 9 and 12 months and corresponding 95% CIs) and a Kaplan-Meier plot will be provided.

#### **9.4.2.3 Analysis of Efficacy Endpoints of the Cross-over Analysis Set**

For the Cross-over Analysis Set, efficacy endpoints include ORR, PFS, DoR, tumour size assessment CCI. Details of the baseline for these endpoints are given in Section 9.4.1. These endpoints will only be summarised descriptively (Section 9.4.2.2).

Listings, and possibly summaries of the above endpoints depending on the number of patients, will be presented for patients who cross-over from savolitinib plus placebo to savolitinib plus osimertinib, presenting data from the baseline of their second phase onwards (see Section 9.4.1).

Further details of how the data for these patients will be presented will be described in the SAP.

#### **9.4.2.4 Exploratory Endpoints**

Statistical analysis of the exploratory endpoints will be summarised in the SAP.

#### **9.4.3 Safety**

Safety and tolerability will be assessed in terms of AEs, SAEs, discontinuation rate due to AEs, deaths, laboratory data, vital signs, ECHO data, ECG data and ECOG performance status. All safety analyses will be performed on the SAS. Data will also be presented separately for patients who crossed over to savolitinib plus osimertinib upon investigator-assessed PD per RECIST 1.1 on savolitinib plus placebo. Safety data will be presented using descriptive statistics unless otherwise specified.

Adverse events will be coded using the most recent version of MedDRA that have been released for execution at AstraZeneca. Adverse events will be graded according to the National Cancer Institute CTCAE (Version 5.0).

The number of patients experiencing each AE will be summarised by the MedDRA system organ class, preferred term and treatment group. The number and percentage of patients with AEs in different categories (eg, causally related, CTCAE Grade  $\geq 3$  etc) will be summarised, and events in each category will be further summarised by MedDRA system organ class, preferred term and treatment group. If there are sufficient SAEs, they will be summarised separately. Further details will be provided in the SAP.

Adverse events occurring prior to the start of study intervention, treatment-emergent AEs and post-treatment emergent AEs will be presented separately. Adverse events occurring in the savolitinib in combination with placebo group will be split into 2 presentations based on whether they occurred before or after the crossover into the savolitinib in combination with osimertinib group.

Any AE occurring before the first dose of study intervention will be included in the data

listings but will not be included in the summary tables of AEs. Adverse event summary tables will include only treatment-emergent AEs. The following events are considered treatment emergent:

- Adverse events with an onset date on or after the first dose of randomised study intervention and within the safety follow-up period (28 days [ $\pm$  7 days] after last dose of all study intervention). Any events in this period that occur after a patient has received further therapy for cancer (following discontinuation of all study intervention) will be flagged in the data listings.
- Worsening of pre-existing events on or after the first dose of study intervention and within the safety follow-up period.

Any events in this period that occur after a patient has received further therapy for cancer (following discontinuation of all study intervention) will be flagged in the data listings, but not included in the summaries.

An overview of AEs will present for each treatment group the number and percentage of patients with any AE, AEs with outcome of death, SAEs, and AEs leading to discontinuation of study intervention, as well as AEs leading to study intervention dose interruptions, and AEs leading to study intervention dose reduction as well as the number of individual occurrences in those categories.

Separate AE tables will be provided taken into consideration relationship as assessed by the investigator, CTCAE grade, seriousness, death and events leading to discontinuation of study intervention for the first 6 weeks and at any time as well as other action taken related to study intervention.

An additional table will present number and percentage of patients with most common AEs. Most common (eg, frequency of  $> x\%$ ,  $\geq x\%$ ) will be defined in the SAP.

In accordance with the requirements of the FDA, a separate table will present non-serious AEs occurring in more than 5% of patients in any treatment group.

Key patient information will be presented for patients with AEs with outcome of death, SAEs, and AEs leading to discontinuation of study intervention.

An AE listing for the SAS will cover details for each individual AE; an AE listing for patients who were not exposed to study intervention is presented separately.

Full details of AE analyses will be provided in the SAP.

During the evaluation of the AE data, an AstraZeneca medically qualified expert will review

the list of AEs that were not reported as SAEs or AEs leading to discontinuation. Based on the expert's judgement, significant AEs of particular clinical importance may, after consultation with the Global Patient Safety Physician, be considered other significant AEs and reported as such in the CSR. A similar review of laboratory/vital signs (pulse and BP)/ECG data will be performed for identification of other significant AEs. Examples of these could be marked haematological and other laboratory abnormalities, and certain events that lead to intervention (other than those already classified as serious), dose reduction or significant additional treatment. Tables and figures for potential Hy's Law cases will be produced.

Duration of exposure will be summarised. The number and percentage of patients with at least one dose interruption/dose delay and at least one dose reduction will also be summarised separately for the first 6 weeks and at any time.

Details of any deaths will be listed for all patients.

Graphical presentations of safety data will be prepared as is deemed appropriate.

Other safety data including physical examinations, clinical haematology, chemistry, urinalysis, vital signs and ECGs will be summarised using descriptive statistics. For all laboratory variables, which are included in the current version of CTCAE, the CTCAE grade will be calculated. The analysis will be performed based on the SAS for the overall population and the Cross-over Analysis Set.

A frequency table presents number of patients reporting at least one treatment emergent changes in laboratory parameters. For all laboratory variables, which are included in the current version of CTCAE, the CTCAE grade will be calculated.

Details of vital sign and laboratory analyses will be provided in the SAP.

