#### **8.3.2.1 Adverse Event Variables**

The following variables will be collected for each AE:

- AE (verbatim)
- The date and time when the AE started and stopped
- The maximum on-treatment CTCAE grade (according to CTCAE Version 5.0)
- Whether the AE is serious or not
- Investigator causality rating against the study interventions (yes or no)
- Action taken with regard to study interventions
- Outcome.

In addition, the following variables will be collected for SAEs:

- Date AE met criteria for SAE
- Date investigator became aware of SAE
- AE is serious due to
- Date of hospitalisation
- Date of discharge
- Probable cause of death
- Date of death
- Autopsy performed
- Causality assessment in relation to study procedure(s)
- Causality assessment to other medication

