#### 9.4.1 General Considerations

Descriptive statistics will be used for all variables as appropriate and will be presented by treatment arm. Continuous variables will be summarised by the number of observations, mean, standard deviation, median, minimum, and maximum. Categorical variables will be summarised by frequency counts and percentages for each category. Unless otherwise stated, percentages will be calculated out of the population total for the corresponding treatment arm.

Results of all statistical analyses will be presented using a 95% CI and p-value, unless otherwise stated.

Additional subgroup analyses of efficacy and safety may be performed and will be specified in the SAP.

Depending on the extent of any impact, summaries of data relating to patients diagnosed with COVID-19, and impact of COVID-19 on study conduct (in particular missed visits, delayed or discontinued study intervention, and other protocol deviations) may be generated. More detail will be provided in the SAP.

Baseline for patients on randomised treatment will be the last assessment of the variable under consideration prior to the intake of the first dose, except for efficacy variables. For efficacy variables, baseline is defined as the last visit prior to randomisation. For patients who cross-over from savolitinib plus placebo to savolitinib plus osimertinib, their data will be cut off for the purposes of any savolitinib plus placebo assessment at the last assessment of the variable under consideration prior to the intake of the first dose of the combination therapy.

Efficacy data will be summarised and analysed on the FAS, safety data will be summarised on the SAS and PK data will be summarised on the PK Analysis Set.

Baseline for ORR, PFS, DoR and tumour size assessments of patients who cross-over to savolitinib plus osimertinib from savolitinib plus placebo will be the progression scan on savolitinib plus placebo, acquired within 28 days of the start of treatment in the cross-over period. CCI

Baseline for safety assessments of patients who cross-over to savolitinib plus osimertinib from savolitinib plus placebo will be set as the last assessment prior to first dose of osimertinib.

A Cross-over Analysis Set is included for patients randomised to savolitinib plus placebo who cross-over to savolitinib plus osimertinib upon objective PD per RECIST 1.1.

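### The adverse event variables collected do not allow the savolitinib plus placebo cut-off to be applied to the grade of an event that worsens after cross-over

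*Supplement*

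**What the plan says.** **Intended separation.** For patients who cross over, Section 9.4.1 of the protocol ties the end of the savolitinib plus placebo data to the first combination dose: "their data will be cut off for the purposes of any savolitinib plus placebo assessment at the last assessment of the variable under consideration prior" (the sentence goes on to name that dose). It also resets the cross-over safety baseline, which "will be set as the last assessment prior to first dose of osimertinib".

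**Split of AEs.** Under Section 9.4.3, AEs in the savolitinib plus placebo arm "will be split into 2 presentations based on whether they occurred before or after the crossover into the savolitinib in combination with osimertinib group".

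**Treatment-emergent rules.** Section 9.4.3 gives two:
- "Adverse events with an onset date on or after the first dose of randomised study intervention and within the safety follow-up period"
- "Worsening of pre-existing events on or after the first dose of study intervention and within the safety follow-up period"

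Both are anchored to the start of study treatment. Neither has a counterpart anchored to the first osimertinib dose at cross-over.

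**What is collected.** For each AE, Section 8.3.2.1 lists "The date and time when the AE started and stopped" and "The maximum on-treatment CTCAE grade (according to CTCAE Version 5.0" (the edition used for grading). It lists no date for that grade and no grade history.

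**Where the grade is used.** Section 9.4.3 plans to summarise "The number and percentage of patients with AEs in different categories (eg, causally related, CTCAE Grade" 3 or higher, among others.

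**Deferral.** Section 9.4.3 leaves the full detail of the AE analyses to the SAP, which is not among the documents shown.

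**The concern.** Section 4.1.2 keeps savolitinib going without a break while osimertinib is added. A patient's time on treatment therefore runs straight through the switch, and a single AE record can span it. If the AE is mild before the switch and severe after it, that record carries an early start date and a late, undated maximum grade. The date belongs to one treatment and the grade to the other.

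What is at stake is the attribution of severe toxicity. The pre-cross-over presentation describes savolitinib plus placebo, and the Cross-over Analysis Set describes the combination. A grade reached on the combination but reported under savolitinib plus placebo would overstate severity in the first and understate it in the second. The number of patients exposed to the problem may be appreciable, because cross-over is offered at progression and also, under Sections 4.1.2 and 4.1.4, to all remaining savolitinib plus placebo patients once the study is unblinded.

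**Working it through.** The plan states no figure on this point, so there is none to reproduce. The check sets the rules against the data and then gives a scale.

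**Step 1: can the cut-off be applied to grade?** Take an AE that is Grade 1 when it starts on savolitinib plus placebo and reaches Grade 3 after the first cross-over osimertinib dose. If it stays a single record, the database holds a start date before the switch, a stop date after it and a maximum of Grade 3. The Section 9.4.1 cut-off needs the highest grade up to the switch (Grade 1), and that value is not among the listed variables.

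**Step 2: does any allocation of that record come out right?**
- By onset: Grade 3 is reported before cross-over and nothing after it.
- In both presentations: Grade 3 is still reported before cross-over.
- After cross-over only: the Grade 1 event on savolitinib plus placebo disappears.

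None gives Grade 1 before and Grade 3 after.

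**Step 3: do the treatment-emergent rules rescue it?** The onset rule is met already at the original start date. The worsening rule concerns events that pre-date study treatment. Neither marks a second emergence at cross-over.

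**Step 4: which AEs are exposed?**
- ECGs are repeated at scheduled cross-over visits (Table 2, Section 8.2.3). CTCAE grades for laboratory variables are calculated from results and analysed for the Cross-over Analysis Set as well (Section 9.4.3). QTc prolongation and liver toxicity can therefore be largely reconstructed.
- Serious events carry the date on which they met the seriousness criteria (Section 8.3.2.1).
- Non-serious AEs graded only by the investigator, such as rash, fatigue or diarrhoea, have no such independent date.

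**Step 5: scale.** If k patients are affected among n in the arm, the Grade 3 or higher percentage shifts by 100 × k / n, provided they have no other Grade 3 or higher event before cross-over. For k = 1:
- n = 28 (planned, Section 9.2): 100/28 = 3.6 points
- n = 20 (assumed): 100/20 = 5.0 points
- n = 14 (assumed): 100/14 = 7.1 points
- n = 10 (assumed): 100/10 = 10.0 points

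Section 9.2 says that the planned number will not be met, so n is below 28 if the 1:1 allocation stays balanced. The number of affected patients is unknown.

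**The case against.** **The protocol does not say that such an AE is counted against savolitinib plus placebo.** A reader might infer that it does. That would require *occurred* to mean first onset, and worsening never to be entered as a new record. The protocol states neither. Section 9.4.1 points the other way, Appendix B 1 allows an AE to be a deterioration of an existing condition, and Section 8.3.5 has aggravated findings at physical examination reported as AEs. This objection stands against the categorical reading. It does not close the gap: those provisions do not say that worsening of an AE already on record gets its own entry and date, and Section 9.4.1 states an aim that the listed variables cannot meet for grade.

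**Allocation rules are SAP content.** This stands as far as allocation goes. But a SAP can only choose how to place a record; it cannot recover a grade history that was never dated. That part belongs to data collection.

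**Many severe events can be traced elsewhere.** This stands in part. Besides the sources in Step 4, Section 6.4 records dates of dose delays and reductions. QTc prolongation, an overlapping toxicity in Appendix I 1.1, is therefore a poor example of the problem. Investigator-graded, non-serious AEs remain.

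**Safety is descriptive.** True: the synopsis says that safety data will not be formally analysed, and AEs are also listed individually. No test or error rate is affected. The listings, however, rest on the same undated grade.

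**Conclusion.** The point holds as a gap between an intended cut-off and the data collected. For an investigator-graded AE that spans cross-over and worsens after it, the grade up to the switch cannot be derived from the variables in Section 8.3.2.1, unless a recording convention outside the protocol already supplies it. The worst grade may therefore be attributed to savolitinib plus placebo and missed in the Cross-over Analysis Set.

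A reader might go further and conclude that the plan makes the combination look safer in the randomised comparison, or that a particular number of patients will be misplaced. The documents do not support either. The direction would favour the combination if AEs are allocated by onset and worsening is not re-recorded, but neither premise is stated. They also give no counts of cross-overs, of AEs ongoing at the switch, or of AEs that worsen later. The only firm scale is per patient: 3.6 points on the arm's Grade 3 or higher rate at the planned 28, rising to 10 points if the arm had 10 (an assumption).

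Efficacy results are untouched. The change is worth making because these descriptive tables are the trial's safety result and the arms are small.

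**What to change.** **Section 8.3.2.1 and the eCRF completion instructions.** Record the CTCAE grade of every ongoing AE at the first cross-over osimertinib dose. Enter any later worsening as a new AE record with its own start date. For patients who have already crossed over, raise a data query on AEs that were ongoing at the switch, before the database is closed.

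**Section 9.4.3 and the SAP.** For the pre-cross-over presentation, use the grade at that dose as the maximum unless a higher grade was reached earlier. Count onset or worsening on or after that dose as treatment-emergent in the Cross-over Analysis Set. State that *occurred* is to be read in this way.

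**Cost.** A few more AE records and queries. Section 9.4.3 also reports numbers of individual occurrences, and these will rise slightly when worsening is re-recorded, so the tables need a note saying so. If sites already enter worsening as a new AE, one sentence stating that convention covers the new-record part of the change for Section 8.3.2.1.
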